8.1.3 Multiple Imputation Analyses

To examine the sensitivity of the results of the primary analysis to departures from the underlying assumptions, additional analyses may be performed using controlled multiple imputation method introduced in [Keene et al 2014](#), [Wan et al 2015](#), [Gottlow et al 2015](#) and further developed by the European Medicines Agency ([Guideline on Missing Data in Confirmatory Clinical](#)) and AstraZeneca ([AZ guidance](#)), which allows for different underlying assumptions to be used.

As with the primary analysis, the sensitivity analyses include all data until participants withdraw from the study regardless of if they discontinue from randomized treatment.

Participants who use restricted medications and early withdrawals from the study will not be imputed as non-responders as for the primary analysis but will be considered as missing. Participants who use restricted medications will be considered as study withdrawers for severe non-compliance to protocol.

An underlying Bernoulli distribution for the status of response (responder or non-responder) is assumed and post study withdrawal events status of response will be imputed conditional upon the treatment group and the observed covariates. This allows various assumptions about the missing data to be analysed by modifying the post-withdrawal model assumption.

The method involves first fitting the logistic regression model to the observed data and then imputing post-withdrawal status of response by calculating the conditional probability of response relating the observed covariates based on various assumptions.

$$\text{logit } (P(Y_{ij} = 1)) = j + \text{Covariates}_i \quad (1)$$

Here i denotes the participant identifier and j denotes the treatment group (benralizumab or placebo). Covariate $_i$ denotes the baseline disease severity and the time of BP diagnosis of the i th participant. Furthermore,

$$p_{ij} = \frac{\exp(j + \text{Covariates}_i)}{1 + \exp(j * \text{Covariates}_i)} \quad (2)$$

The imputed status of response that would have been seen is then combined with the observed responses and data will be analysed using the primary analysis methodology. This analysis is repeated multiple times and the results combined using Rubin's rules [Rubin 1987, Bernard et al 1999].

The following default assumptions that will be used to impute the missing data who withdraw early from the study are as follows:

- (a) MAR: Missing response status in each treatment group are imputed assuming the expected response rate within that treatment group.
- (b) Dropout Reason-based Multiple Imputation (DRMI): Missing status will be imputed differently depending on the reason for dropout; statuses for participants in the benralizumab treatment group who dropped out for a treatment related reason are imputed based on the expected response rate in the placebo treatment group, whereas the remaining participants who have dropped out are imputed assuming MAR. Treatment related reasons include (1) AEs, (2) Death and (3) Development of study specified reasons to stop active treatments, and (4) severe non-compliance of protocol.

Some reasons for withdrawal are clearer to determine as treatment related (AEs, death, development of study-specific discontinuation criteria) or non-treatment related (participant lost to follow up, eligibility criteria not fulfilled). Other reasons are less clear such as severe non-compliance of protocol, participant decision and 'Other'; a review of each participant who withdraws from the study will therefore be carried out prior to unblinding the study. The review will include assessment of the reason for discontinuation of randomised treatment for those participants who discontinued randomised treatment and then withdrew from the study and also free text for when the reason for withdrawal or discontinuation of randomised treatment is recorded as participant decision or other. Based on this review the default assumptions for DRMI as described in b) and Table 9 may be changed. A list of these participants and the assumptions made under DRMI will be documented prior to unblinding of the study.

A summary of reasons for participants withdrawing from the study and the corresponding treatment group used to calculate the imputation response rate under MAR and DRMI is given in Table 9.

Table 9 Summary of reasons for participants withdrawing from the study and the corresponding treatment group used to calculate the imputation response rate under MAR and DRMI

Reason for withdrawal	MAR	DRMI
Adverse Event	Benralizumab	Placebo
Development of study-specific discontinuation criteria	Benralizumab	Placebo
Death	Benralizumab	Placebo
Severe non-compliance to protocol	Benralizumab	Placebo
Eligibility criteria not fulfilled	Benralizumab	Benralizumab
Participant lost to follow up	Benralizumab	Benralizumab
Participant decision	Benralizumab	Based on review prior to study unblinding
Other	Benralizumab	Based on review prior to study unblinding

Note all participants on response rate in the placebo treatment group are imputed using the placebo treatment group rate

Together with the primary analysis, the sensitivity analyses are considered to cover the range from realistic to plausible worst-case assumptions about missing data.

The DRMI approach has been selected as a conservative approach based on the fact that placebo participants are receiving standard of care and are not expected to change to a substantially more effective treatment after withdrawing from study or study treatment. For participants receiving benralizumab who withdraw from the study due to treatment related reasons it is assumed that at worst they would be on the standard of care treatment, i.e., the placebo treatment group. For participants receiving benralizumab who withdraw from the study due to non-treatment related reasons it seems reasonable to assume they would be similar to those participants who complete treatment.

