Participants who are treated with OCS and then tapered can be at risk for acute adrenal insufficiency. The possibility of acute adrenal insufficiency should be considered, according to the guidance in [Appendix G](#), in any acutely unwell participant undergoing withdrawal of chronic systemic corticosteroid treatment. Assessment of hypothalamic-pituitary-adrenal axis integrity may be performed, according to standard of care, at the discretion of the Investigator.

If the Investigator is considering addition of an immunosuppressant for the treatment of BP relapse, a discussion with the designated study physician should occur to review study options which may include discontinuation of IP. If in the opinion of the Investigator, a participant requires the addition of immunosuppressants for control of relapse, the participant will discontinue IP administration. Participants who are in the double-blind period will be asked to complete all visits and study assessments up to Week 36. Participants who are in the OLE will withdraw from the study and will be asked to complete the study assessments for the final follow-up visit as outlined in the SoA ([Table 2](#)).

While OCS compliance will be captured daily on the handheld device (unless exempted), the main source of data for analysis of OCS-related endpoints will be saved in the eCRF.

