## 9.2 Sample Size Determination

The sample size calculation was derived for the primary endpoint, the proportion of participants who are in complete remission while off OCS for  $\geq 2$  months at Week 36.

Approximately 60 participants are needed per treatment group to detect a 30% difference between benralizumab and placebo with 90% power. The calculation is based on a 2-sided test and a 5% significance level and assumes a response rate of 50% for benralizumab and 20% for placebo.

There is limited evidence currently available from completed comparative BP trials to date to base the study size assumptions on. However, a mepolizumab Phase 2 trial with a similar

participant population, design, and steroid taper rate reported a low proportion who were relapse free up to 36 weeks (20% versus 33% for mepolizumab versus placebo; [Simon et al 2020](#)). From this study, the assumption that an expected remission rate off steroids at Week 36 would be low, at most 20%, was extrapolated. A 30% improvement in this remission rate was recommended by a panel of BP experts to be at the lower end of what may be clinically meaningful, and so was considered to be a conservative assumption.

A non-binding interim futility analysis will be performed by an Independent Data Monitoring Committee (IDMC) when approximately 36 randomized participants (ie, when approximately 30% of the total amount of statistical information is available) have had the opportunity to complete at least 36 weeks of follow-up. By conducting the interim analysis, the overall power will not be affected substantially. Full details are provided in Section [9.5](#).

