1.3 Number of subjects

Approximately 140 participants will be enrolled/screened in order to achieve approximately 100 eligible study participants randomly assigned to study intervention.

The sample size calculation was derived for the primary endpoint, the proportion of participants who are in complete remission while off OCS for ≥ 2 months at Week 36.

Approximately 50 participants are needed per treatment group to detect a 30% difference between benralizumab and placebo with 85% power. The calculation is based on a 2-sided test and a 5% significance level and assumes a response rate of 50% for benralizumab and 20% for placebo.

There is limited evidence currently available from completed comparative BP trials to date to base the study size assumptions on. However, a mepolizumab Phase 2 trial with a similar participant population, design, and steroid taper rate reported a low proportion of patients relapse free up to 36 weeks (20% versus 33% for mepolizumab versus placebo; [Simon et al 2020](#)). From this study, the assumption that an expected remission rate off steroids at Week 36 would be low, at most 20%, was extrapolated. A 30% improvement in this remission rate was recommended by a panel of BP experts to be at the lower end of what may be clinically meaningful, and so was considered to be a conservative assumption.

A non-binding interim futility analysis will be performed by an Independent Data Monitoring Committee (IDMC) when approximately 36 randomized participants (ie, when approximately 36% of the total amount of statistical information is available) have had the opportunity to complete at least 36 weeks of follow-up. By conducting the interim analysis, the overall power will not be affected substantially. Full details are provided in Section [5](#).

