8.1.4 Tipping point analyses

To examine the impact of missing data, including the impact of non-responder/not relapse free imputations due to study withdrawal, for the primary and first key secondary endpoint respectively, tipping point analyses may be performed. These analyses will systematically vary the assumptions about outcomes among the subsets of participants on the treatment arms who withdraw from the study early or have missing data at Week 36 for any other reason.

Tipping point analyses are intended to identify the point at which the results would tip from statistically significant to not statistically significant. Thus, the tipping point analyses will only be performed if an endpoint achieves a nominally statistically significant result (ie, nominal p-value < 0.05).

The analyses will be performed following below steps:

- The proportions of participants non-responder/not relapse free will be analysed using a Pearson's chi-squared test, thus the stratification factors that are used in the main analysis will be disregarded. Since the strata will be balanced in respect of treatment assignment by virtue of the stratified randomisation scheme used, the only impact of this simplification should be that the inferences from the unstratified analysis will be somewhat conservative.
- For the primary analysis, participants who withdraw from the study early or have missing data at Week 36 for any other reason are by definition imputed as non-responders. For this sensitivity analysis, these participants will be altered from non-responder to responder in an iterative manner.
- At each step of the analysis one of these participants switches from not being responder to being responder, and the Pearson's chi-squared test is re-run. The results (statistical significance) are presented in a grid where the x-axis and the y-axis represent the number of participants assumed to be responder for placebo and benralizumab, respectively. The region where the conclusion changes, will be considered as the tipping point.
- The grid will be divided in 3 regions, limited in the top by the expected number of participants with missing values in the benralizumab treatment group which would have been responder if observed at Week 36 (based on the proportion of responders in participants who did not withdraw from the study early or have missing data at Week 36 for any other reason in the benralizumab treatment group):

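### The MAR and DRMI analyses impute response for restricted-medication users who are non-responders under the primary estimand, and the tipping-point steps can flip recorded relapses

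*SAP*

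**What the plan says.** **Primary estimand.** SAP 3.2 and Table 8 handle restricted-medication use and study withdrawal with a composite strategy: both are non-response. SAP 3.1.5.2 limits this to medications confirmed as intercurrent events before unblinding. Protocol 6.5.1 keeps a participant who needs an immunosuppressant under observation: "Participants who are in the double-blind period will be asked to complete all visits and study assessments up to Week 36".

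**Multiple imputation.** SAP 8.1.3 sets both groups to missing and adds: "Participants who use restricted medications will be considered as study withdrawers for severe non-compliance to protocol". Response is drawn from a logistic model with treatment arm, baseline disease severity and time of diagnosis. MAR uses the participant's own arm's rate. DRMI uses the placebo rate for benralizumab participants whose reason counts as treatment related, and Table 9 puts severe non-compliance in that class by default. Table 11 repeats MAR and DRMI on on-treatment data.

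**Tipping point.** SAP 8.1.4 covers the primary and the relapse-free endpoints. The switching takes place "among the subsets of participants on the treatment arms who withdraw from the study early or have missing data at Week 36 for any other" cause, one participant at a time.

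**What is claimed.** SAP 8.1.3 says that, taken together with the primary analysis, "the sensitivity analyses are considered to cover the range from realistic to plausible worst-case assumptions about missing data". SAP 8.1.8 will read similar estimates as assurance that lost information does not materially affect the primary conclusion.

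**The concern.** A missing-data sensitivity analysis should hold the estimand fixed and vary only what is assumed about unobserved outcomes. Under a composite strategy the outcome of a restricted-medication user is not unobserved: the event itself makes it a non-response, whether or not the participant attends Week 36. Section 8.1.3 reopens that outcome. If MAR or DRMI then differs from the primary analysis, or agrees with it, the reader cannot tell whether the cause is the missing data or the changed handling of restricted medication.

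The relapse-free endpoint has a parallel problem. A participant who relapsed or took OCS rescue and later withdrew is known not to be relapse-free. Section 8.1.4 aims to examine failures imputed because of withdrawal, but its steps select on withdrawal or missing Week 36 data alone. The grid can then contain outcomes that could not have occurred.

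At stake is the robustness evidence for the primary and first key secondary results, not the primary test or the testing hierarchy.

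**Working it through.** **Base case.** The plan gives no figure for this point, so I take its planning rates: the sample size "assumes a response rate of 50% for benralizumab and 20% for placebo", and "Approximately 50 participants are needed per treatment group to detect a 30% difference between benralizumab and placebo with 85% power". Fisher's exact test by full enumeration gives 85.3% power at 50 per arm. It gives 91.3% at the protocol's 60 per arm, where 90% is stated. Both figures reproduce with an exact test; the pooled normal formula gives 89.4% and 94.1%. The base case is therefore 25/50 versus 10/50, a difference of 30.0 points.

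The documents give no rate for restricted-medication use or withdrawal. All such counts below are assumptions. Calculations are expected rates on the risk-difference scale, without covariates.

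**Step 1: nobody withdraws, so nothing is missing.** Let p be the composite response rate and f the share of an arm using restricted medication.

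- MAR as written: rate = p/(1 − f) in each arm.
- DRMI as written: benralizumab rate = p_B + f_B × p_P/(1 − f_P); placebo rate = p_P/(1 − f_P).
- Failures retained: 50% versus 20%, 30.0 points, whatever f is.

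| f benralizumab / placebo | MAR (points) | DRMI (points) |
|---|---|---|
| 5% / 5% | 31.6 | 30.0 |
| 10% / 10% | 33.3 | 30.0 |
| 20% / 20% | 37.5 | 30.0 |
| 20% / 10% | 40.3 | 32.2 |
| 10% / 20% | 30.6 | 27.5 |
| 10% / 25% | 28.9 | 26.0 |

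With complete data, the so-called missing-data analyses still depart from 30.0: MAR in every row, DRMI whenever the arms differ.

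**Step 2: add 5 withdrawals per arm.**

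Restricted use 8 (benralizumab) versus 3 (placebo), so 13 and 8 are set to missing:

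- MAR as written: 25/37 − 10/42 = 67.6% − 23.8% = 43.8 points.
- MAR with failures retained: 25/45 − 10/45 = 33.3 points.
- DRMI as written, all reasons treatment related: (25 + 13 × 0.2381)/50 − 0.2381 = 56.2% − 23.8% = 32.4 points.
- DRMI with failures retained: (25 + 5 × 0.2222)/50 − 0.2222 = 52.2% − 22.2% = 30.0 points.
- DRMI with none of the 5 withdrawals treatment related: (25 + 8 × 0.2381 + 5 × 0.6757)/50 − 0.2381 = 36.8 points as written, against 33.3 with failures retained.

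Restricted use 3 versus 8, so 8 and 13 are set to missing:

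- MAR as written: 25/42 − 10/37 = 32.5 points.
- DRMI as written, all treatment related: (25 + 8 × 0.2703)/50 − 0.2703 = 27.3 points.
- DRMI as written, no withdrawal treatment related: (25 + 3 × 0.2703 + 5 × 0.5952)/50 − 0.2703 = 30.5 points.
- Failures retained: unchanged at 33.3 (MAR) and 30.0 to 33.3 (DRMI).

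The excess over the retained version is 10.5 points under MAR and 2.4 to 3.4 under DRMI in the first case. In the second, both analyses fall below it.

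**Step 3: tipping point for relapse-free.** Assume 30/50 versus 17/50, no benralizumab withdrawals, and 6 placebo withdrawals of whom 4 had a recorded relapse. Pearson's chi-squared without continuity correction:

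| Placebo flips | Placebo relapse-free | p |
|---|---|---|
| 0 | 17/50 | 0.009 |
| 2 | 19/50 | 0.028 |
| 3 | 20/50 | 0.046 |
| 4 | 21/50 | 0.072 |

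As written, up to 6 flips are allowed and significance is lost at the 4th. Only 2 outcomes are unknown, and at 2 flips the result holds. The upper limit of the Uncertain region is 6 × 30/50 = 3.6 as written and 2 × 30/50 = 1.2 with recorded relapses kept. The Likely limit is 6 × 17/44 = 2.3 as written and 2 × 17/48 = 0.7 with them kept.

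**The case against.** The case for leaving the text alone has substance.

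- **The change is partly disclosed.** Section 8.1.3 states that these participants are handled differently from the primary analysis, and Table 11 lists MAR MI and DRMI in its estimand row. This stands, but the results are still to be read as assurance about missing data.
- **The claimed range includes the primary analysis.** Table 11 also has an on-treatment analysis that keeps restricted medication, withdrawal and treatment dropout as non-response, and a treatment-policy analysis that keeps withdrawals as non-response. A reader might infer that none of the planned analyses tests the primary result. The documents do not support that; the problem lies in MAR, DRMI and their on-treatment versions.
- **DRMI is the harsher rule.** It shrinks the excess to about 2 to 3 points and can disfavour benralizumab. An inference that the analyses systematically favour benralizumab is therefore unsupported: the direction depends on the event imbalance.
- **Relapse is not failure for the primary endpoint.** Under SAP 3.2 a participant who needs more OCS, tapers again and meets the remission criteria by Week 36 is a responder. A reader might infer that any relapse before withdrawal is an observed primary failure; it is not.
- **The tipping-point example tips in the Unlikely region,** since the 4th flip lies beyond 3.6. Extra placebo flips make the result look less robust, so this defect does not conceal fragility. The steps do not name restricted medication either; such users are flipped only if they also withdraw or lack Week 36 data.
- **The stakes are limited.** The imputation and tipping-point analyses are optional, SAP 4.2.7.2 expects restricted-medication use to be infrequent, and SAP 8.1.8 foresees an update before primary database lock. Against that expectation, 8 of 50 (16%) is a high assumed count.

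What remains is that 8.1.3 states an explicit rule rather than leaving a gap. It also sits badly with its own preceding statement that the sensitivity analyses use all data until study withdrawal.

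**Conclusion.** The point holds in limited form. MAR and DRMI in SAP 8.1.3, with their on-treatment versions, do not isolate the missing-data assumption, because they give participants who failed under the composite estimand a non-zero chance of response. In the illustrations the effect on the difference is 1.6 points (MAR, 5% restricted use in each arm, no withdrawals) to 10.5 points (MAR, 8 versus 3 with 5 withdrawals per arm). DRMI moves by 2.4 to 3.4 points in that second setting and falls below the retained version when placebo has more events. All of these rest on assumed event counts.

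Separately, the 8.1.4 steps applied to the relapse-free endpoint admit impossible cells and inflate the region limits whenever a withdrawal had already relapsed, taken OCS rescue or used restricted medication. The aim stated in that section suggests this was not intended, so a clarification is enough. Neither matter affects the primary test. Both weaken the inference that SAP 8.1.8 intends to draw, and both should be corrected before unblinding.

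**What to change.** - **SAP 8.1.3 and Table 11:** keep restricted-medication users, on the intercurrent-event list of SAP 3.1.5.2, as non-responders in the MAR and DRMI analyses. Impute only withdrawals or missing Week 36 outcomes without prior restricted-medication use. If the present version is wanted, keep it as a separately labelled hypothetical estimand.
- **SAP 8.1.4:** limit the flips, and the counts and proportions behind the region limits, to participants whose failure comes only from imputation. For the primary endpoint this means no restricted medication before withdrawal; for relapse-free, no relapse, OCS rescue or restricted medication before withdrawal.

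The SAP already draws this line elsewhere: 3.3.1 for the timing of relapse in withdrawals, and 4.2.7.3 for the BPDAI imputation. The cost is a few sentences and one programming flag from data already collected, and it fits the SAP update already planned before primary database lock.

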8.1.4 Tipping point analyses

To examine the impact of missing data, including the impact of non-responder/not relapse free imputations due to study withdrawal, for the primary and first key secondary endpoint respectively, tipping point analyses may be performed. These analyses will systematically vary the assumptions about outcomes among the subsets of participants on the treatment arms who withdraw from the study early or have missing data at Week 36 for any other reason.

Tipping point analyses are intended to identify the point at which the results would tip from statistically significant to not statistically significant. Thus, the tipping point analyses will only be performed if an endpoint achieves a nominally statistically significant result (ie, nominal p-value < 0.05).

The analyses will be performed following below steps:

- The proportions of participants non-responder/not relapse free will be analysed using a Pearson's chi-squared test, thus the stratification factors that are used in the main analysis will be disregarded. Since the strata will be balanced in respect of treatment assignment by virtue of the stratified randomisation scheme used, the only impact of this simplification should be that the inferences from the unstratified analysis will be somewhat conservative.
- For the primary analysis, participants who withdraw from the study early or have missing data at Week 36 for any other reason are by definition imputed as non-responders. For this sensitivity analysis, these participants will be altered from non-responder to responder in an iterative manner.
- At each step of the analysis one of these participants switches from not being responder to being responder, and the Pearson's chi-squared test is re-run. The results (statistical significance) are presented in a grid where the x-axis and the y-axis represent the number of participants assumed to be responder for placebo and benralizumab, respectively. The region where the conclusion changes, will be considered as the tipping point.
- The grid will be divided in 3 regions, limited in the top by the expected number of participants with missing values in the benralizumab treatment group which would have been responder if observed at Week 36 (based on the proportion of responders in participants who did not withdraw from the study early or have missing data at Week 36 for any other reason in the benralizumab treatment group):
 - Likely – Its right limit is the expected number of participants with missing values in the placebo arm which would have been responder if observed at Week 36 (based on the proportion of responders in participants who did not withdraw from the study early or have missing data at Week 36 for any other reason in the placebo treatment group);
 - Uncertain – its right limit is the expected number of participants with missing values in the placebo treatment group which would have been responder if observed at Week 36 (based on the proportion of responders in participants who did not withdraw from the study early or have missing data at Week 36 for any other reason in the benralizumab treatment group);
 - Unlikely – It is the region to the right of the uncertain region.

